Founded in 2014, the Stanford South Asian Translational Heart Initiative (SSATHI) is the only preventive cardiology clinic in the U.S. dedicated to exclusively treating South Asian patients for both traditional and non-traditional cardiovascular risk factors. The clinic includes an intensive program combining physician visits and serial laboratory testing. The patients also benefit from frequent dietitian/health coach visits during the program, all of which are conducted virtually through SSATHI's telehealth arm, CardioClick. Typically, lipid lowering effects from lifestyle changes are manifest within 3 months. In this proposal, the study length will be 3 months for each enrolled subject.

Study Design

This single arm study will include one in-person or video baseline visit, with a virtual follow up visit with the treating physician.

At the baseline visit, subjects will complete informed consent, a medical history, and clinic visit procedures, inclusion/exclusion criteria, medication review, measurement of morphometrics (body weight, height, BMI, hip and waist circumference, blood pressure, heart rate). A fasting blood draw for baseline labs will be performed within 8 weeks of start date. Women under 60 years will receive a urine pregnancy test. We are washing out any lipid lowering non prescription medications.

There will also be focused patient engagement questionnaires administered at the end of the study.

Intervention

Enrolled subjects, upon completion of the baseline clinical and laboratory assessment, will be given a 90 day supply of gummy plant sterol supplements in daily packets, totaling 1400 mg of daily plant sterol to be ingested in two daily doses. During the 90 day treatment, subjects will be contacted weekly through Twilio or SMS messaging by the research team to assess compliance which requires a single digit response from each subject to report compliance with the gummy sterol treatment. At the end of the study, a virtual clinical visit and laboratory test, along with post-study surveys, will be administered.

Baseline visit

- Informed consent/HIPAA
- Medical history
- Clinic visit
 - Baseline measurements, lab testing
 - Assess prior and current medication/supplement use
 - Review inclusion/exclusion criteria
- Diet assessment
- Fasting Lipid profile
- In-clinic urine pregnancy test for female subjects, if applicable
- Dispense study product
- Provide study instructions

Regular product compliance assessment

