6. Individual has a condition the Investigator believes would interfere with his or her ability to provide informed consent, comply with the study protocol, which might confound the interpretation of the study results or put the person at undue risk.

Primary Outcome

% change in LDL Direct, or LDL-C if LDL Direct is not available, from baseline at 3 months

Exploratory Outcomes

% changes from baseline to 3 months in following:

- Total cholesterol
- Calculated LDL-C or LDL Direct
- HDL-C
- Non-HDL-C
- Triglycerides
- Fasting Glucose
- Fasting Insulin
- Hba1c
- Lp(a)
- Apoprotein B-100
- Apoprotein A1
- Ratio, ApoB-100/Apo A1
- C-reactive protein

Changes from baseline to 3 months in questionnaire metrics of patient engagement, satisfaction, and outlook on health

Product compliance

Subjects' interest in continuing to use product

Statistical Analysis

Because of the pre-post nature of this single group study, either a paired t-test or a non-parametric paired test will be employed to analyze the statistical significance of any differences at the end of the study. This decision will depend upon the normality of the data set.

Sample Size

A sample size of 50 will be enrolled. Our population exhibits a standard deviation of 25mg/dl in baseline LDL-C, the primary outcome variable. As a result, an evaluable sample of 40 subjects will provide 80% power to detect a difference of 10% based on a paired t-test and a two-sided alpha of 0.05. A larger enrolled sample will allow for subject attrition of up to 20%.

Statistical Analysis

Baseline characteristics will be described using means and standard deviations or medians and interquartile range limits as appropriate based on the distribution for continuous variables. Numbers of subjects and percentages will be used to describe categorical variables. Responses to the intervention will be assessed using paired t-tests for continuous variables. For categorical variables, McNemar's test will be employed to assess differences in frequencies between baseline and end-of-study. All tests of statistical significance will be completed using alpha = 0.05, two-sided.

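### Could the primary LDL change be computed from two different LDL methods in the same subject?

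*Combined protocol and SAP*

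**What the plan says.** The Primary Outcome section defines the endpoint in one line: the percentage "change in LDL Direct, or LDL-C if LDL Direct is not available, from baseline at 3 months". The Exploratory Outcomes section lists percentage changes over the same period, and one of its items is "Calculated LDL-C or LDL Direct".

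The Baseline visit and End of Study Visit lists both name the same test, "Fasting Lipid profile". Neither names LDL Direct as a separate assay. Under Study Design, "A fasting blood draw for baseline labs will be performed within 8 weeks of start date". Under Intervention, "At the end of the study, a virtual clinical visit and laboratory test, along with post-study surveys, will be administered".

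The first Statistical Analysis section says that "either a paired t-test or a non-parametric paired test will be employed", depending on normality. The second says "Responses to the intervention will be assessed using paired t-tests for continuous variables". Neither mentions pairs in which the LDL method differs between visits.

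**The concern.** The fallback to LDL-C shows that the authors expected LDL Direct to be missing for some data. They did not say what happens when it is missing at one visit only. Applied visit by visit, the rule would take the direct value where there is one and the calculated value where there is not. Some subjects' percentage change would then contain the difference between two methods as well as any biological change.

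The setting makes this conceivable. The baseline sample may be drawn up to 8 weeks before the start, the end-of-study visit is virtual, and nothing requires the same LDL test on both occasions. The design would not absorb the error: "This single arm study will include one in-person or video baseline visit" and has no control group, so a net one-way switch adds directly to the estimated effect. If switching lowered apparent LDL, it would favour the supplement. A rule left open could also be settled after the data are seen.

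**Working it through.** **Step 1: the wording.** The Primary Outcome line has three possible readings.

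- *Per subject:* percentage change in LDL Direct if it exists at both visits, otherwise percentage change in LDL-C. No cross-method pairs.
- *Whole trial:* LDL Direct for everyone if the trial has it, otherwise LDL-C for everyone. No cross-method pairs.
- *Per visit:* whichever value exists at each visit. Cross-method pairs arise when LDL Direct exists at one visit only.

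In the sentence, LDL Direct and LDL-C are parallel objects of a single percentage change from baseline. Each names a change variable. A change in LDL Direct cannot be formed from one direct value, so in that case LDL Direct is unavailable as a change and the fallback is the change in LDL-C. The per-visit reading needs a quantity the sentence does not name: one measure at 3 months relative to a different measure at baseline. The exploratory item "Calculated LDL-C or LDL Direct" sits in a list of changes in named measures, which fits the first two readings better than the third.

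**Step 2: the data needed for the fallback.** A fasting lipid profile is listed at both visits. For a subject with LDL Direct at one visit only, a same-method LDL-C change should normally be available.

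**Step 3: size under the per-visit reading.** The plan gives no figure on this point to reproduce. Inputs:

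- From the Sample Size section: 40 evaluable subjects (50 × (1 − 0.20) = 40), two-sided alpha 0.05, target difference 10%, SD of baseline LDL-C 25 mg/dL.
- Assumed: mean LDL 145 mg/dL; method difference *m* of 1 to 10 mg/dL; net share *f* of subjects switching, all in one direction; no true effect; SD of percentage change *s* of 14 or 17.2 points. The 17.2 is 25/145, which borrows the baseline SD for the change.

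Formulas:

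- Shift per switched subject: b = 100 × m/145. This gives 0.69, 1.38, 3.45 and 6.90 points for m = 1, 2, 5 and 10.
- Bias in the mean: f × b.
- SD with switching: √(s² + b² f(1 − f)).
- Two-sided rejection rate: noncentral t, 39 degrees of freedom, noncentrality √40 × f × b / SD.

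Example: m = 10, f = 0.25, s = 14. Bias = 0.25 × 6.90 = 1.72 points. SD = √(196 + 47.6 × 0.1875) = 14.3. Noncentrality = 6.325 × 1.72/14.3 = 0.76. Rejection rate 11.5%.

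| Method difference | 10% switch: bias; rate | 25% switch: bias; rate | 50% switch: bias; rate |
|---|---|---|---|
| 1 mg/dL | 0.07; 5.0% | 0.17; 5.0–5.1% | 0.34; 5.2–5.3% |
| 2 mg/dL | 0.14; 5.0% | 0.34; 5.2–5.3% | 0.69; 5.7–6.1% |
| 5 mg/dL | 0.34; 5.2–5.3% | 0.86; 6.1–6.7% | 1.72; 9.4–11.7% |
| 10 mg/dL | 0.69; 5.7–6.0% | 1.72; 9.4–11.5% | 3.45; 22.8–31.4% |

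Bias is in percentage points. Each range of rates covers the two SDs. A simulation of 100,000 trials per cell for the 5 and 10 mg/dL rows agrees to within one percentage point.

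**Step 4: break-even.** Ignoring the small rise in SD, a two-sided rate of 10% needs a bias of 1.48 points (SD 14) or 1.82 points (SD 17.2). At 10 mg/dL the net one-way share is 1.48/6.90 = 21% or 1.82/6.90 = 26%. At 5 mg/dL it is 1.48/3.45 = 43% or 1.82/3.45 = 53%.

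**Step 5: direction.** If as many subjects switch one way as the other, the bias is zero and the simulated false-positive rate is 3.7–5.0%. If net switching raises apparent LDL, false findings of benefit fall to 1.8% or less, against 2.5% nominal.

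**The case for a change.** The strongest case for acting is that no sentence requires one method per subject, this is the primary endpoint, the error would not cancel, and one clause would settle it using tests already scheduled. Non-HDL-C and ApoB-100 do not depend on the LDL method, but they are exploratory and cannot decide the primary value.

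Most of this is right as description. The text is silent, and a clause using LDL Direct only when it exists at both visits, and LDL-C at both otherwise, would do no harm. Silence is not a faulty rule, though. That clause writes down what the sentence already says on its ordinary reading and what an analyst running a paired test would do. A count of subjects by method and a sensitivity analysis on calculated LDL-C are sound practice but are not needed to make the endpoint correct.

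The larger false-positive rates do not change this. The 31% cell needs half the subjects to switch, all in one direction, with a 10 mg/dL difference and the smaller SD. Other assumptions would move the top of the range either way. With an SD of 12 points, a 10% method difference and 50% one-way switching, the rate is 66%. The documents support none of these inputs, so the figures show what could happen under a strained reading and do not measure a defect in the plan.

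**Conclusion.** No change is called for. The primary outcome line leaves out a detail, but its ordinary reading gives same-method pairs, and the lipid profile scheduled at both visits supplies the data for the fallback. Bias requires three things together: the per-visit reading, a material difference between methods, and switching that is frequent and mostly in one direction. The documents point to none of the three.

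Even on the per-visit reading, a 10% one-way share moves the mean by no more than 0.7 points for method differences up to 10 mg/dL, and the two-sided false-positive rate is about 6% at most. That rests on an assumed mean LDL of 145 mg/dL, an SD of percentage change of 14–17.2 points, and 40 evaluable subjects. The true size cannot be known from the documents and may be nil. The conclusion rests mainly on the wording; the arithmetic only shows that modest switching would matter little.

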- Weekly Twilio or SMS text messaging question with a numeric response to assess product compliance

End of Study Visit

- Assess prior and current medication/supplement use
- Fasting Lipid profile
- Questionnaire
 - SSATHI questionnaire
 - Sponsor questionnaire
- Assess product compliance
- Assess adverse events

Inclusion Criteria

1. Subject is a South Asian male or female, ≥ 18 years of age
2. Subject has LDL-C ≥ 120 and < 190 mg/dL measured in the past 3 months (or measured at the baseline visit), while not taking cholesterol-lowering medication or cholesterol-lowering supplement for at least 1 month prior, and having a ASCVD Risk score $< 7.5\%$.
3. Subjects with LDL-C ≥ 120 and < 190 mg/dL with ASCVD risk scores $> 7.5\%$ who are known to be intolerant of statin therapy drugs.
4. Subjects with LDL-C > 189 mg/dL or ASCVD $> 7.5\%$ who have declined prescription medical therapy.
5. If current smoker, subject does not have any plans to change current smoking status or frequency.
6. Subject is willing to fast (10-14 h, target 12 h, water only) prior to each clinic visit.
7. Subject understands the study procedures and signs forms documenting informed consent to participate in the study and authorization for release of relevant protected health information to the study Investigator and is willing to complete study procedures.
8. Subject is agreeable to receiving clinical care virtually.

Exclusion Criteria

1. Subject has taken a prescription cholesterol-lowering medication in the past 1 month.
2. Subject has a known allergy or sensitivity to soy, corn, or other ingredients in the study product.
3. Subject is taking dietary supplements for cholesterol-lowering such as red yeast rice, niacin > 100 mg/d or omega-3 fatty acid supplements providing ≥ 1000 mg/d eicosapentaenoic acid and/or docosahexaenoic acid. (Stable use of viscous fiber laxative ≤ 2 teaspoons/d is allowed.)
4. Subject is a female, who is pregnant, planning to be pregnant during the study period, or lactating. Subjects should agree to use contraception during study period to avoid pregnancy.

5. Individual has active angina, stable or unstable, requiring urgent cardiovascular functional risk stratification (stress testing or catheterization) or intervention. Or has congestive heart failure that is not compensated or in which the subject is not euvolemic, as determined by the treating MD.

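### An exploratory outcome is defined as change from baseline in questionnaire scores, but the plan schedules the questionnaires only at the end of study, so as written no change can be computed.

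*Combined protocol and SAP*

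**What the plan says.** The Exploratory Outcomes section includes "Changes from baseline to 3 months in questionnaire metrics of patient engagement, satisfaction, and outlook on health".

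Three places say when questionnaires are given:

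- Study Design: "There will also be focused patient engagement questionnaires administered at the end of the study".
- Intervention, describing the end of the study: "a virtual clinical visit and laboratory test, along with post-study surveys, will be administered".
- End of Study Visit list: "SSATHI questionnaire" and "Sponsor questionnaire".

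Neither the Study Design account of the baseline visit nor the Baseline visit list names a questionnaire. The nearest baseline item is a diet assessment. Between visits, the weekly text message asks only about compliance.

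For analysis, the first Statistical Analysis section says that "either a paired t-test or a non-parametric paired test will be employed". The second gives paired t-tests for continuous variables and McNemar's test for categorical ones. The Sample Size section plans 50 enrolled and "an evaluable sample of 40 subjects".

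**The concern.** A change from baseline needs the same instrument at two times. The plan describes one administration, after treatment. A site that followed the visit descriptions exactly would not collect what the outcome list promises, and the analyst would find no baseline value to subtract.

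Timing makes this more than a wording matter. Product is dispensed at the baseline visit, so once that visit is over a pre-exposure response is lost for that subject. The conflict has to be settled before enrolment, or the outcome has to be redefined.

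**Working it through.** The check is mainly a comparison of the outcome definition with the schedule.

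| Source | Baseline | During treatment | End of study |
|---|---|---|---|
| Outcome definition (Exploratory Outcomes) | required | – | required |
| Study Design text | no questionnaire named | – | engagement questionnaires |
| Intervention text | – | weekly compliance reply | post-study surveys |
| Visit lists | diet assessment only | weekly compliance question | SSATHI and Sponsor questionnaires |

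**Pairs available.** Each subject has 0 baseline and 1 end-of-study administration. The number of pairs is 0 whether n = 40 or n = 50. The paired t-test, a non-parametric paired test and McNemar's test all work on within-subject pairs, so none can be run on these items.

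**Weight of the evidence.** The sentences in Study Design and Intervention state the timing directly and carry the argument. The visit lists agree with them: the item "Assess prior and current medication/supplement use" and the fasting lipid profile appear at both visits, the questionnaires at one. That agreement is secondary, because the lists are not exhaustive. The end-of-study list names only a lipid profile, although changes in glucose, insulin, HbA1c and other laboratory values are also planned.

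The plan gives no figure of its own for this outcome. The following shows what each remedy would deliver, assuming that every evaluable (or every enrolled) subject completes the questionnaires.

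**If a baseline is added.** Paired t-test, two-sided alpha 0.05, power 80%. The normal approximation to the detectable change, in SDs of the change score, is d = (1.960 + 0.842)/√n.

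- n = 40: 2.802/6.325 = 0.443; with the noncentral t distribution, 0.454.
- n = 50: 2.802/7.071 = 0.396; with the noncentral t distribution, 0.404.

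**If the outcome stays end-of-study only.** Wilson 95% interval for a proportion p, with n = 40 and z = 1.96 (z² = 3.8416):

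- Centre = (p + z²/2n)/(1 + z²/n).
- Half-width = z√[p(1−p)/n + z²/4n²]/(1 + z²/n).
- Here z²/2n = 0.0480, z²/n = 0.0960 and z²/4n² = 0.0006.
- 20/40: centre 0.5480/1.0960 = 0.500; half-width 1.96 × √0.00685/1.0960 = 0.148; interval 0.352 to 0.648.
- 32/40: centre 0.8480/1.0960 = 0.774; half-width 1.96 × √0.00460/1.0960 = 0.121; interval 0.652 to 0.895.

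The proportions 50% and 80% are illustrations, not figures from the plan.

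**The case against.** The strongest reply is that the text never says the questionnaires are given *only* at the end, and the instruments are not shown. They might ask subjects to compare themselves with their state before the study, or the clinic might collect similar information routinely, so that some report of change could come from one administration. This is possible, but the plan says neither. If either is intended, the plan has to state it, and a recalled change would still not supply pairs for the tests it names.

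Second, the Study Design sentence names engagement only, and the Intervention sentence does not say what its surveys contain. That the SSATHI and Sponsor questionnaires carry the satisfaction and outlook items is an inference. This stands as a caution, but no other text places those two domains at baseline, so it does not supply the missing measurement.

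Third, the visit lists are a weak guide, since laboratory outcomes needed twice are not all listed at the end-of-study visit. This is correct, and the conclusion does not rest on absence from a list.

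Fourth, the power and interval figures do not measure the defect, and the outcome is exploratory. Both are fair. The figures bear only on the choice of remedy, and the exploratory status limits the importance of the point without removing the contradiction.

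**Conclusion.** The concern holds. As written, one exploratory outcome line covering three domains (engagement, satisfaction, outlook on health) has one scheduled time point where two are needed, and neither a change score nor a paired test can be formed. The conclusion rests on the documents as they stand, with no retrospective items and no routine baseline collection described.

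The reach is limited. The primary LDL outcome has a fasting lipid profile at both visits, and the sample size does not depend on the questionnaires. The general McNemar sentence is not wrong in itself and may serve other variables; it simply cannot apply to items collected once. The plan should be corrected, because an uncollected baseline cannot be recovered.

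**What to change.** Choose one option and make Study Design, Intervention, the two visit lists and Exploratory Outcomes agree.

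1. **Add a baseline administration.** At the baseline visit, before product is dispensed, give those engagement and outlook items that make sense before exposure, and use the same instrument at the end. Report product satisfaction and interest in continuing as end-of-study summaries, for example a proportion with its 95% interval, since satisfaction with a product has no value before it is used. The cost is a short questionnaire at a visit that already takes place. Its length, and whether the existing instruments contain suitable items, are assumptions because the instruments are not shown.
2. **Restate the outcome.** Drop the change-from-baseline wording and describe all three domains at end of study. This is a wording change only, but it gives up any measure of change.

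The general McNemar sentence need not be deleted under either option.

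### The 80% power claim rests on the between-subject SD of baseline LDL-C; a paired test needs the SD of within-subject change, which the plan does not give

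*Combined protocol and SAP*

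**What the plan says.** The Sample Size section gives one measure of variability and draws the power from it directly: "Our population exhibits a standard deviation of 25mg/dl in baseline LDL-C, the primary outcome variable. As a result, an evaluable sample of 40 subjects". The full claim is that "an evaluable sample of 40 subjects will provide 80% power to detect a difference of 10% based on a paired t-test". The alpha is 0.05, two-sided. Fifty subjects are to be enrolled, to allow for up to 20% attrition.

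Under Primary Outcome, the variable is the percentage "change in LDL Direct, or LDL-C if LDL Direct is not available, from baseline at 3 months". It is not baseline LDL-C.

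The two Statistical Analysis sections do not fix the scale of the test. The first says "either a paired t-test or a non-parametric paired test will be employed to analyze the statistical significance of any differences", with the choice depending on normality. The second says "Responses to the intervention will be assessed using paired t-tests for continuous variables". Neither states whether the test is run on percentage changes or on mg/dL values.

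**The concern.** A paired t-test is a one-sample test on each subject's change, so its power depends on the mean change divided by the SD of that change. The SD of baseline values describes how subjects differ from one another. It determines the SD of change only when combined with the follow-up SD and the pre-post correlation, and the plan states neither.

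The units do not match either. The effect is a percentage and the SD is in mg/dL, with no mean LDL-C to connect them.

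What is at stake is the planning justification, because this sentence is the only reason given for 40 evaluable subjects. A reader of a null result would lean on the 80% to judge what had been ruled out. The observed p-value and the confidence interval for the mean change are unaffected, and the interval would still show whether a 10% change is compatible with the data.

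**Working it through.** **Inputs from the document.** n = 40 evaluable, two-sided alpha 0.05, target difference 10%, SD of baseline LDL-C 25 mg/dL (Sample Size and Statistical Analysis). Inclusion criteria 2 and 3 bound LDL-C at 120 to below 190 mg/dL. Criterion 4 sets no LDL-C floor for its ASCVD route. The plan states no mean, no correlation and no SD of change, so the values used for these below are assumptions.

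**Method.** Exact power of a paired t-test from the noncentral t distribution, with 39 degrees of freedom and noncentrality d × √40, where d = mean change / SD of change. Power of 80% requires d = 0.4543.

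**Attempts to reproduce the 80%.**

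1. Read 10 and 25 on one scale: d = 10/25 = 0.40, noncentrality 0.40 × √40 = 2.53, power **69.4%**. Power of 80% would need n = 52.
2. Take 25 mg/dL as the SD of change and 10% of an assumed mean as the effect:
   - mean 120: 12/25 = 0.48, power 84.1%
   - mean 140: 14/25 = 0.56, power 93.2%
   - mean 155: 15.5/25 = 0.62, power 96.9%
   - 80% is reached only at a mean of 0.4543 × 25 / 0.10 = 113.6 mg/dL, below the floor in criteria 2 and 3
3. Repeat step 1 with a one-sided 0.05 test: 79.97%. This matches numerically, but the plan specifies two-sided testing. Whether the figure was obtained this way cannot be known from the document.

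The attrition step does reproduce: 50 × 0.8 = 40.

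**On the endpoint's own scale.** For a 10-point mean percentage change, 80% power at n = 40 requires an SD of percentage change of at most 10/0.4543 = 22.0 points. The last three columns give the correlation each SD would imply if the SD were 25 mg/dL at both visits. Since SD of change = 25 × √(2(1 − ρ)), ρ = 1 − (SD/100 × mean)² / 1250. This treats 10% as 10% of the mean, so the correlations are approximate; the power column does not depend on that step.

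| Assumed SD of % change | Power, n = 40 | n for 80% | ρ, mean 120 | ρ, mean 140 | ρ, mean 155 |
|---|---|---|---|---|---|
| 15 | 98.4% | 20 | 0.74 | 0.65 | 0.57 |
| 20 | 86.9% | 34 | 0.54 | 0.37 | 0.23 |
| 22 | 80.0% | 40 | 0.44 | 0.24 | 0.07 |
| 25 | 69.4% | 52 | 0.28 | 0.02 | −0.20 |
| 30 | 53.8% | 73 | −0.04 | −0.41 | −0.73 |

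Example for one cell: SD 22, mean 120 gives (0.22 × 120)² / 1250 = 26.4² / 1250 = 0.558, so ρ = 0.44.

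**Non-parametric alternative.** With the signed-rank test on normally distributed percentage changes (20,000 simulated trials per row), power at the same five SDs is about 98%, 85%, 78%, 67% and 52%.

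**The case against.** The strongest reply is that power may well be adequate and that what is missing is an assumption, not a correct sum. If 25 mg/dL is the SD at each visit, 80% needs a correlation of only about 0.44 at a mean of 120, 0.24 at 140 and 0.07 at 155. A mean of 120 is itself pessimistic: it is the floor for criteria 2 and 3, so it could arise only with subjects admitted below that floor through criterion 4. The 69% figure also divides a percentage by a value in mg/dL, and the plan never puts those on one scale. The signed-rank figures assume normal data, although the plan reserves the non-parametric test for non-normal data.

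Most of this stands as a limit on the conclusion. Power below 80% requires a low correlation, a mean near the eligibility floor or a follow-up SD above 25 mg/dL, and the 69% shows a failed reproduction rather than the true power. The signed-rank figures are only a rough guide.

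It does not rescue the claim. Using the baseline SD as the SD of change assumes a correlation of exactly 0.5 with equal SDs. That is optimistic at any lower correlation, and it still does not return 80% at any mean of 120 or above. The plan presents as unconditional a result that depends on a quantity it never states.

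**Conclusion.** The concern holds. The 80% cannot be derived from the stated inputs, and baseline LDL-C is wrongly labelled as the primary outcome variable. With 40 evaluable subjects, power for a 10-point mean change runs from 98% to 54% as the SD of percentage change goes from 15 to 30 points, and equals 80% only at about 22 points. Those SDs, and the means and correlations used to interpret them, are assumptions because the document gives none.

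This is not evidence that the trial is underpowered. It is a defect in the only sample-size rationale. It should be corrected, but it does not affect the validity of the analysis.

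**What to change.** Keep 50 enrolled and 40 evaluable, the endpoint and the tests. In the Sample Size section, remove the words that call baseline LDL-C the primary outcome variable. Then replace the power sentence with one of two versions.

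**(A) If an SD can be estimated.** The section The Clinic says "The clinic includes an intensive program combining physician visits and serial laboratory testing", so repeat LDL values may already exist.

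> The SD of 3-month percentage change in LDL is [value] points ([source]). With 40 evaluable subjects, a two-sided 0.05 paired t-test has 80% power for a mean change of [0.454 × SD] points.

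If that SD exceeds 22.0 points, the detectable change exceeds 10 points. The text should then say so and also give the power for 10 points.

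**(B) If no estimate exists.** Drop the unconditional 80% and label the figures as a sensitivity table:

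> No estimate of the SD of 3-month percentage change was available. As a sensitivity table: for assumed SDs of 15, 20, 22, 25 and 30 points, 40 evaluable subjects give 98%, 87%, 80%, 69% and 54% power for a 10-point mean change (t-test, two-sided 0.05).

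The 22-point row is solved back from 80% and must not be presented as a planning assumption unless data support it.

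In either version, state that the calculation refers to a test on percentage change.

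The cost is one reworded paragraph and, for (A), a look-up in the clinic's laboratory results. No extra subjects are needed. The downside is that the stated power may become less favourable.
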